9.2.1. Inclusion criteria

All births from 1 January 2005 through 31 December 2015 (both dates inclusive) in Denmark, Finland, and Norway and all births identified from 1 July 2006 through 31 December 2016 (both dates inclusive) in Sweden.

9.2.2. Exclusion criteria

Patients meeting any of the following criteria will be excluded from the study:

1. Births with exposure to known teratogenic medications during the first trimester;
2. Births with a chromosomal abnormality diagnosis.

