8. RESEARCH QUESTION AND OBJECTIVES

The study objectives are to:

1. Describe the use of gabapentin in pregnancy.
2. Estimate the risk of major congenital malformations, other birth outcomes, and selected postnatal neurodevelopmental outcomes of pregnancies with exposure to gabapentin as compared with pregnancies with: no exposure to antiepileptic drugs (AEDs); exposure to pregabalin; exposure to lamotrigine; exposure to pregabalin or lamotrigine.

The primary objectives of the study are to:

- Describe use of gabapentin, pregabalin, and lamotrigine during pregnancy overall (for any therapeutic use), and by:
 - trimester of pregnancy,
 - indication,
 - cumulative dose,
 - calendar year of delivery;

Description of exposure will be performed for all pregnancies, including pregnancies with monotherapy exposure (defined as no concomitant administration with other AEDs) and pregnancies with polytherapy exposure (defined as concomitant administration with other AEDs), as well as the subset of only pregnancies with monotherapy exposure.

- Calculate the prevalence of major congenital malformations in pregnancies with first-trimester exposure to:
 - gabapentin;
 - pregabalin;
 - lamotrigine;
 - pregabalin or lamotrigine.
- Perform a sensitivity analysis to calculate the prevalence of major congenital malformations that includes stillbirth and pregnancies ending in therapeutic 2nd trimester induced abortion in the definition of prevalence in pregnancies with first-trimester exposure to:
 - gabapentin;
 - pregabalin;
 - lamotrigine;
 - pregabalin or lamotrigine.
- Estimate the associations between first-trimester exposure to gabapentin and prevalence of major congenital malformations, as compared with:
 - no exposure to AEDs during the first trimester;
 - exposure to pregabalin during the first trimester;
 - exposure to lamotrigine during the first trimester;
 - exposure to pregabalin or lamotrigine during the first trimester.
- Calculate the prevalence of pre-specified birth outcomes including stillbirth, low birth weight, small for gestational age (SGA), preterm birth, low Apgar score, microcephaly, among pregnancies with any trimester exposure to:
 - gabapentin;
 - pregabalin;
 - lamotrigine;
 - pregabalin or lamotrigine.

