9.3. Variables

9.3.1. Exposures

For the purposes of identifying timing of exposure, trimesters of pregnancy will be defined as follows:

Gabapentin

A9451182 NON-INTERVENTIONAL STUDY PROTOCOL

Final, 02 October 2020

- First trimester: LMP-90 days to LMP+97 days (both dates inclusive);
- Second trimester: from LMP+98 days to LMP+202 days (both dates inclusive);
- Third trimester: from LMP+203 days (inclusive) until pregnancy end date (not included).

LMP, depending on country is either directly recorded in the birth registry or estimated from gestational age. LMP will be determined using the following hierarchy/availability: ultrasound determined LMP (if recorded), self-reported LMP (if ultrasound-reported is unavailable); date of delivery minus gestational age in days (if LMP unavailable by ultrasound or self-report). If gestational age is missing, LMP will be imputed by subtracting 280 days from date of delivery.

Exposure during the first trimester

Gabapentin exposure during the first trimester is defined as at least one maternal dispensing of gabapentin during the first trimester.

Comparators/reference groups:

No exposure to AEDs-This reference group consists of births with no maternal dispensing of any AED during the first trimester.

Pregabalin exposure in the first trimester is defined by at least one maternal dispensing of pregabalin during the first trimester. Pregabalin monotherapy in the first trimester will be defined as first-trimester exposure to pregabalin and no first-trimester dispensing for any other AED.

Lamotrigine exposure in the first trimester is defined by at least one maternal dispensing of lamotrigine during the first trimester. Lamotrigine monotherapy in the first trimester will be defined as first-trimester exposure to lamotrigine and no first-trimester dispensing for any other AED.

Pregabalin or lamotrigine exposure in the first trimester is defined by at least one maternal dispensing of pregabalin and/or lamotrigine during the first trimester. Pregabalin or lamotrigine monotherapy in the first trimester will be defined as first-trimester dispensing of pregabalin and/or lamotrigine and no first-trimester dispensing for any other AED.

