9.5. Study size

Table 3 shows estimated number of total pregnancies ending in live or stillbirth and pregnancies with AED exposure (any use, i.e., pregnancies exposed to monotherapy and pregnancies exposed to polytherapy).

Table 3. Estimated numbers of pregnancies ending in live or still birth (any use, i.e., pregnancies exposed to monotherapy and pregnancies exposed to polytherapy)*

	Denmark (2005-2016)	Finland (2005-2016)	Norway (2005-2016)	Sweden (2006-2016)	TOTAL
Live/still births	728,052	701,550	717,219 (657,451)	1,152,002	3,298,823

Table 3. Estimated numbers of pregnancies ending in live or still birth (any use, i.e., pregnancies exposed to monotherapy and pregnancies exposed to polytherapy)*

	Denmark (2005-2016)	Finland (2005-2016)	Norway (2005-2016)	Sweden (2006-2016)	TOTAL
Pregnancies with dispensation of Gabapentin, first trimester	374	374	344	500	1,592
Gabapentin, any time during pregnancy	388	388	467	500	1,743
Pregabalin, first trimester	372	1,020 (935)	248 (227)	1,230	2,870
Pregabalin, any time during pregnancy	377	1,053 (965)	225 (307)	1,275	2,930
Lamotrigine, first trimester	2,266	1,048 (961)	1,841 (1,688)	2,838	7,993
Lamotrigine, any time during pregnancy	2,379	1,104 (1,012)	2,110 (1,934)	2,991	8,584

*Number of exposed in Denmark and Sweden are the actual numbers for 2005-2016; estimated for Finland and Norway based on 2005-2015 data in parenthesis. No exclusion criteria are applied in this table.

The 2005-2016 estimated numbers of pregnancies ending in live or still birth for potentially analysis-relevant categories for Norway and Finland were unavailable at the time of writing the protocol but are estimated using data from 2005-2015 to provide the most conservative estimate.^{14,45,46,47}

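### The exclusions in 9.2.2 apply to the whole study, so the primary objective of describing drug use, polytherapy included, is answered in a cohort already selected on co-medication

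*Protocol*

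**What the plan says.** Section 9.2.2 opens with "Patients meeting any of the following criteria will be excluded from the study" and lists two criteria: "Births with exposure to known teratogenic medications during the first trimester" and "Births with a chromosomal abnormality diagnosis". Section 9.3.1 defines the first trimester as running from 90 days before the last menstrual period (LMP) to 97 days after it, so a dispensing before conception is enough to exclude a birth.

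Section 8 lists the description of gabapentin, pregabalin and lamotrigine use among the primary objectives, overall and by trimester, indication, cumulative dose and year. It adds: "Description of exposure will be performed for all pregnancies, including pregnancies with monotherapy exposure", and it names "pregnancies with polytherapy exposure (defined as concomitant administration with other AEDs") as part of that group. Section 9.7.4.1 implements this as the number and proportion of births exposed, with monotherapy reported as well. It sits under 9.7.4, which sets one analysis population for all primary analyses and none specific to drug use.

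**The concern.** The two exclusions serve the outcome contrasts. A known teratogen would confound a malformation comparison, and a chromosomal anomaly is not a plausible drug effect. Neither reason applies to a count of how often a drug was dispensed in pregnancy.

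The teratogen criterion is the one that matters. A user of a study drug who is removed for having received another, teratogenic drug is by definition co-medicated, and co-medication is one of the things the objective sets out to describe. An analyst following 9.2.2 would drop these births before tabulating use. The rule looks only at the first trimester, but it removes the birth from the any-trimester tables too. The study is a regulatory commitment, and its readers would receive a use description for a narrower population than section 8 suggests, with no count of who was left out.

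**Working it through.** **Scope of the exclusion, from the text.** The protocol limits an exclusion to particular analyses when it means to:

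- Section 9.3.1 ties the removal of certain co-exposed pregnancies to the analyses that use a named comparator.
- Section 9.2 removes Norwegian births before 2008 for the neurodevelopmental analysis only.
- Section 9.2.2 carries no such limit, and neither 9.7.4 nor 9.7.4.1 restores the births it removes.

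Read together, these sections put the drug-use tables after the exclusions.

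**Inputs.** Table 3 gives the only exposed counts, before exclusions. Its columns for Denmark, Finland and Norway run to 2016, one year past 9.2.1, so the counts serve here only to show scale. The totals add up:

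- Births: 728,052 + 701,550 + 717,219 + 1,152,002 = 3,298,823.
- Gabapentin, first trimester: 374 + 374 + 344 + 500 = 1,592.
- Gabapentin, any time: 388 + 388 + 467 + 500 = 1,743.

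The share f of exposed births that would be excluded is not given. Every value of f below is an assumption.

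**Effect on counts.** Births removed = f × exposed births.

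- First-trimester gabapentin, f = 5% to 20%: 0.05 × 1,592 = 80; 0.20 × 1,592 = 318.
- First-trimester lamotrigine, same f: 0.05 × 7,993 = 400; 0.20 × 7,993 = 1,599.

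Any-time gabapentin use before exclusions is 1,743 / 3,298,823 = 0.528 per 1,000 births. With the denominator held fixed:

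| f | Births removed | Use per 1,000 |
|---|---|---|
| 1% | 17 | 0.523 |
| 5% | 87 | 0.502 |
| 10% | 174 | 0.476 |
| 20% | 349 | 0.423 |

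The denominator also shrinks in practice. If a share r of all births is excluded, the reported proportion is the true one × (1 − f)/(1 − r). The count falls whenever f is above zero; the proportion falls only if f exceeds r.

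**Effect on the polytherapy share.** Let q be the true share of polytherapy among users, g the fraction of polytherapy births removed and h the fraction of monotherapy births removed. The reported share is q(1 − g) / [q(1 − g) + (1 − q)(1 − h)].

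Suppose removals come only from polytherapy (h = 0), as they would if the listed drugs were other AEDs. With an assumed q = 30%:

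- g = 10%: 0.27 / 0.97 = 27.8%
- g = 25%: 0.225 / 0.925 = 24.3%
- g = 50%: 0.15 / 0.85 = 17.6%

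If the list holds only drugs that are not AEDs, h is no longer zero. With h = g the share does not move, and otherwise its direction depends on which of the two is larger.

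**Effect on outcome precision.** Table 4 gives 1.465 for any major malformation, gabapentin against unexposed. The formula exp{(1.960 + 0.842) × √[(1 − p)/(n₁p) + (1 − p)/(n₀p)]} with p = 0.03, n₁ = 1,743 and n₀ = 3,297,080 gives 1.465, matching the plan. Removing 10% of the exposed births gives 1.495. The harm is to the drug-use objective; the comparisons lose little precision.

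**The case against.** The strongest reply is that all pregnancies in section 8 is only a label for monotherapy plus polytherapy, set against the monotherapy subset. Section 8 uses the same words for the prevalence and incidence calculations, where the exclusions belong, so the phrase alone cannot mean before exclusions. That is fair, and the point is therefore not an outright contradiction. It rests on the study-wide scope of 9.2.2 and on the absence of any separate population for the use tables.

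Second, the list of known teratogenic medications is not in the body text, and neither the Annex 3 codes nor Figure 1 is shown. Whether AED polytherapy is cut at all depends on that list. This stands, so the polytherapy effect is conditional. The understated counts do not need an AED on the list; they need only one user who meets a criterion.

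Third, the design clearly expects polytherapy births to remain: eight of the sixteen propensity-score sets in 9.7.3.1 include them, and AEDs are a covariate in 9.3.3. This is also true. The issue is partial and selective removal, with polytherapy still present.

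Fourth, describing use in the cohort that supplies the outcome estimates keeps use tables and denominators in agreement. That is a real advantage, and reporting the excluded numbers beside the use tables preserves it.

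**Conclusion.** As written, the plan answers a primary objective in a cohort restricted by a criterion that selects on co-medication. Exposed counts will be understated if any user meets either criterion. Understated polytherapy and an overstated monotherapy share follow only if the teratogen list includes another AED. The chromosomal criterion has no place in a use description, but it does not select on co-medication and its effect is probably small. The size of the loss cannot be derived from the protocol. At an assumed 1% it is trivial and at 20% it is not, so the figures above are illustrative only.

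A reader might go further in three ways that the document does not support:

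- **Lamotrigine worst affected.** No section gives co-dispensing by drug. The larger lamotrigine numbers above reflect only its larger exposed group.
- **Biased dose and indication distributions.** Nothing in the protocol gives a direction or a size for this.
- **Table 3 in error for showing counts before exclusions.** The table says so itself: "No exclusion criteria are applied in this table".

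**What to change.** In 9.2.2, limit both exclusions to the outcome analyses: prevalence, incidence, comparative and sensitivity analyses. The crude outcome prevalences in 9.7.4.1 stay on the restricted cohort.

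In 9.7.4.1, state that the drug-use tables (trimester, indication, cumulative dose, year, monotherapy and polytherapy) cover all births in 9.2.1 before exclusions. Add, for each drug, the number later excluded, by reason and by mono/polytherapy, so that use tables and outcome denominators can be reconciled. Small cells fall under the protocol's existing rule on fewer than five events.

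The cost is about two sentences of text and a few table rows from data already held. No comparative estimate changes.

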9.3. Variables

9.3.1. Exposures

For the purposes of identifying timing of exposure, trimesters of pregnancy will be defined as follows:

Gabapentin

A9451182 NON-INTERVENTIONAL STUDY PROTOCOL

Final, 02 October 2020

- First trimester: LMP-90 days to LMP+97 days (both dates inclusive);
- Second trimester: from LMP+98 days to LMP+202 days (both dates inclusive);
- Third trimester: from LMP+203 days (inclusive) until pregnancy end date (not included).

LMP, depending on country is either directly recorded in the birth registry or estimated from gestational age. LMP will be determined using the following hierarchy/availability: ultrasound determined LMP (if recorded), self-reported LMP (if ultrasound-reported is unavailable); date of delivery minus gestational age in days (if LMP unavailable by ultrasound or self-report). If gestational age is missing, LMP will be imputed by subtracting 280 days from date of delivery.

Exposure during the first trimester

Gabapentin exposure during the first trimester is defined as at least one maternal dispensing of gabapentin during the first trimester.

Comparators/reference groups:

No exposure to AEDs-This reference group consists of births with no maternal dispensing of any AED during the first trimester.

Pregabalin exposure in the first trimester is defined by at least one maternal dispensing of pregabalin during the first trimester. Pregabalin monotherapy in the first trimester will be defined as first-trimester exposure to pregabalin and no first-trimester dispensing for any other AED.

Lamotrigine exposure in the first trimester is defined by at least one maternal dispensing of lamotrigine during the first trimester. Lamotrigine monotherapy in the first trimester will be defined as first-trimester exposure to lamotrigine and no first-trimester dispensing for any other AED.

Pregabalin or lamotrigine exposure in the first trimester is defined by at least one maternal dispensing of pregabalin and/or lamotrigine during the first trimester. Pregabalin or lamotrigine monotherapy in the first trimester will be defined as first-trimester dispensing of pregabalin and/or lamotrigine and no first-trimester dispensing for any other AED.

9.3.2. Outcomes

For each outcome defined below, the population (denominator), period of pregnancy identification, and follow-up for outcome assessment are described in [Table 1](#).

Table 1. Types of pregnancies included in analysis of each outcome for the primary analyses, secondary analyses, and sensitivity analyses

Outcome	Study population and period of pregnancy identification				Follow-up for outcome assessment
	Denmark	Finland	Norway	Sweden	
Primary analyses	Major congenital malformations (overall and specific)	Pregnancies ending in singleton/multiple live birth, stillbirth, 1Jan2005 - 31Dec2015 inclusive		Pregnancies ending in singleton/multiple live birth or stillbirth 1Jul2006-31Dec2016 inclusive	Prevalence at birth with outcomes identified at birth, and until the first birthday (inclusive) through 2016 in Denmark, Finland and Norway and through 2017 in Sweden
	Stillbirth	Pregnancies ending in singleton/multiple live birth, stillbirth, 1Jan2005 - 31Dec2015 inclusive		Pregnancies ending in singleton/multiple live birth or stillbirth 1Jul2006-31Dec2016 inclusive	Prevalence at birth
	Low birth weight SGA ¹³	Pregnancies ending in singleton/multiple live birth, 1Jan2005 - 31Dec2015 inclusive		Pregnancies ending in singleton/multiple live birth 1Jul2006-31Dec2016 inclusive	Prevalence at birth
	Preterm birth				
	Low Apgar score at 5 minutes				
Secondary analyses	Microcephaly				
	Attention-deficit hyperactivity disorders	Pregnancies ending in singleton/multiple live birth, 1Jan2005 - 31Dec2015 inclusive	Pregnancies ending in singleton/multiple live birth, 1Jan2008 - 31Dec2015 inclusive	Pregnancies ending in singleton/multiple live birth 1Jul2006-31Dec2016 inclusive	Minimum 1 year postnatally. Maximum available postnatally, 31Dec 2016 Denmark, Finland, Norway; 31Dec 2017 Sweden.
	Pervasive developmental disorders				
Sensitivity analyses	Learning disorders and intellectual disabilities				
Sensitivity analyses	Major congenital malformations (overall and specific) including malformations identified prenatally	Pregnancies ending in singleton/multiple live birth, stillbirth, 1Jan2005 - 31Dec2015 inclusive and pregnancies ending in therapeutic 2 nd trimester induced abortion, 1Jan2005-31Dec2015 inclusive (Denmark, Norway) 31Dec2012 (Finland)		None	Prevalence at birth with outcomes identified prenatally, at birth, and until the first birthday (inclusive) through 2016 in Denmark and Norway and 31Dec2016 in Finland

Table 1. Types of pregnancies included in analysis of each outcome for the primary analyses, secondary analyses, and sensitivity analyses

Outcome		Study population and period of pregnancy identification				Follow-up for outcome assessment
		Denmark	Finland	Norway	Sweden	
Sensitivity analyses	Major congenital malformations (overall)	Pregnancies ending in singleton/multiple live birth, stillbirth, 1Jan2005 - 31Dec2015 inclusive		Pregnancies ending in singleton/multiple live birth or stillbirth 1Jul2006-31Dec2016 inclusive		Prevalence of major congenital malformation events for each of the 2 gabapentin dispensing categories of '1 dispensing', and '>1 dispensing'.

SGA, Small for gestational age; ADHD, attention deficit hyperactivity disorder; ASD, autism spectrum disorders.

* In the Patient Registry of Norway, the source of data for the postnatal outcomes has existed from 2008.

9.3.2.1. Primary Outcomes (Birth outcomes)

- Major congenital malformations, any and specific malformation type, according to the EUROCAT classification¹⁴
- Stillbirth, as recorded in each country's birth registry
- Low birth weight (birth weight < 2500 g)
- Small for gestational age (SGA), defined, for singleton pregnancies, as a dichotomous variable (yes/no) of birth weight below 2 standard deviations (SDs) of sex- and gestational week specific distributions, using country-specific reference standard.^{13,15} SGA non-singleton gestations will be defined if appropriate reference standard can be defined/identified; otherwise set to missing.
- Preterm birth, defined as gestational age <37 weeks
- Low Apgar score at 5 minutes, defined as a dichotomous variable (score 0-6 vs. score 7-10)
- Microcephaly, defined as a dichotomous variable (yes/no) of head circumference at birth (cm) smaller than 2 SD of sex- and gestational week specific distribution, using country-specific reference standard

9.3.2.2. Secondary Outcomes (Postnatal neurodevelopmental outcomes)

Postnatal neurodevelopmental outcomes (ICD-10 (International Classification of Diseases, Tenth Revision) codes):

- Attention-deficit hyperactivity disorders (F90);
- Pervasive developmental disorders (autism spectrum disorders) (F84);

- Learning disorders (Specific developmental disorders of speech and language (F80), and Specific developmental disorders of scholastic skills (F81)) and Intellectual disabilities (mental retardation) (F70-F79).

Follow-up for the postnatal neurodevelopmental outcomes, when available, will be a minimum of 1 year postnatally and for the maximum period available in the dataset for each birth. However, for a variety of reasons (e.g. emigration, death), follow-up could be infeasible in individual cases. It should be noted that not all livebirths will have available follow-up information into the school age, and as postnatal neurodevelopmental disorders are diagnosed primarily at school age, the number of events in gabapentin exposed (and other comparator groups) pregnancies in the study period may not be sufficient to yield stable estimates of association.¹⁶

9.3.2.3. Sensitivity Analysis (Major congenital malformations)

The analyses of major congenital malformations (overall, not for specific malformations due to expected low counts) will be repeated with the inclusion of pregnancies ending in 2nd trimester therapeutic induced abortions (in all countries except Sweden, where data on pregnancies ending in 2nd trimester therapeutic induced abortions is unavailable).

Some patients may have obtained a single dispensing (prescription) of an antiepileptic drug. Possible reasons for this may be that the drug was prescribed for an indication other than epilepsy, treatment was stopped due to an adverse reaction, etc. Two (2) gabapentin dispensing categories of '1 dispensing', and '>1 dispensing', will be used to stratify select descriptive analyses of major congenital malformations (it is anticipated that patient counts will not be high enough to support stratified comparative analyses). The definition that will be used in the primary analyses is at least 1 dispensing. If patient counts within both these dispensing categories are sufficiently high, the number of major congenital malformation events, the total number of newborns at risk and the prevalence of major congenital malformation events for each of the 2 gabapentin dispensing categories will be provided. As noted above, given the very small sample size of gabapentin first trimester-exposed pregnancies ending in a live or still birth, and the low prevalence of major congenital malformations, it will not be feasible to conduct any further stratified analyses (i.e., analyses simultaneously stratified by dispensing and other variables).

